4.3.6 RAVE data collection

RAVE is the NCI-DCP approved Electronic Data Management System (EDM)

Medidata Rave is a clinical data management system being used for data collection for this trial/study. Access to the trial in Rave is controlled through the CTEP-IAM system and role assignments.

Requirements to access Rave via iMedidata:

- A valid CTEP-IAM account; and
- Assigned a Rave role on the LPO or PO roster at the enrolling site of: Rave CRA, Rave Read Only, Rave CRA (LabAdmin), Rave SLA, or Rave Investigator.

Rave role requirements:

- Rave CRA or Rave CRA (Lab Admin) role must have a minimum of an Associate Plus (AP) registration type;
- Rave Investigator role must be registered as an Non-Physician Investigator (NPIVR) or Investigator (IVR); and
- Rave Read Only role must have at a minimum an Associates (A) registration type.

Refer to <https://ctep.cancer.gov/investigatorResources/default.htm> for registration types and documentation required.

Upon initial site registration approval for the study in RSS, all persons with Rave roles assigned on the appropriate roster will be sent a study invitation e-mail from iMedidata. To accept the invitation, site users must log into the Select Login (<https://login.imedidata.com/selectlogin>) using their CTEP-IAM user name and password, and click on the “accept” link in the upper right-corner of the iMedidata page. Please note, site users will not be able to access the study in Rave until all required Medidata and study specific trainings are completed.

Trainings will be in the form of electronic learnings (eLearnings), and can be accessed by clicking on the link in the upper right pane of the iMedidata screen. If an eLearning is required and has not yet been taken, the link to the eLearning will appear under the study name in iMedidata instead of the Rave EDC link; once the successful completion of the eLearning has been recorded, access to the study in Rave will be granted, and a Rave EDC link will display under the study name.

Users that have not previously activated their iMedidata/Rave account at the time of initial site registration approval for the study in RSS will also receive a separate invitation from iMedidata to activate their account. Account activation instructions are located on the CTSU website, Rave tab under the Rave resource materials (Medidata Account Activation and Study Invitation Acceptance). Additional information on iMedidata/Rave is available on the CTSU members’ website under the Rave tab at [www.ctsu.org/RAVE/](http://www.ctsu.org/RAVE/) or by contacting the CTSU Help Desk at [name] or by e-mail at [[contact]](mailto:[contact]).

## 5. Methodology Plan

We will conduct an observational study to compare 1) the proportion of COVID-related participant factors (including financial hardship and distress among WOC who decline participation in TMIST (EAQ201 participants) compared to non-WOC EAQ201 participants; and 2) effects of federal-, state- and local-level COVID-19 factors on TMIST participation, in WOC vs non-WOC. The primary objective compares COVID-related financial hardship between WOC vs non-WOC EAQ201 participants (see **Table 1** definition). Federal-, state-, local-, practice- and participant-level moderators (see Fig. 1 conceptual model) will be evaluated with hierarchical regression models. For the exploratory objectives, we will compare the effects of federal-, state- and local-level COVID-related factors on TMIST participation (secondary outcome), stratified by WOC vs non-WOC. Any woman 45-74 years old who is scheduled for breast cancer screening and is eligible for TMIST but declines will be approached by the TMIST site research associates (RAs). Enrollment for TMIST typically occurs immediately prior to the scheduled breast screening visit. Solicitation for participation in EAQ201 will occur at the same time for those who decline TMIST. TMIST site RAs will ask women who decline TMIST if they are interested in participating in EAQ201.

Sites participating in the parent study may approach potential participants using written materials, by phone or at the time of screening mammography. We will use the same enrollment processes. For those who are approached by phone and who decline to participate in TMIST will be recruited for EAQ201 during the same call.

For those sites that use the written materials, it is up to the participant to actively respond to the site at which point they are additionally screened for eligibility for TMIST, usually by phone. Among those who respond to written materials and are additionally screened by phone, we will be able to approach the women who decline to participate in TMIST for EAQ201 recruitment.

Paper documentation of consent is required. It may be signed when the participant attends the scheduled screening mammogram.

We will also compare the sociodemographic characteristics of women who complete the EAQ201 participant survey with women who agree to participate in TMIST over the same time period using only data collected as part of the TMIST study that have also been collected as part of the current study. No additional data will be collected from women who participate in the TMIST study.

No additional participant-level data will be collected from TMIST participants related to COVID-19 given the supplement scope. We elected to more completely understand the effects of COVID-19 on those who declined participation in TMIST.

Site characteristics and recruitment process: All sites will receive \$30 per-case reimbursement for each eligible participant who registered to EAQ201. As with EAQ162CD, the study will provide some resources to assist the site, in particular: 1) site RA guides for engaging women who decline TMIST to enhance EAQ201 participation; 2) biweekly webinars/ phone calls for sites to check-in and discuss issues regarding recruitment and/or other study related issues, as needed. Sites that have implemented successful recruitment processes will be encouraged to attend and share their experiences.

Site Recruitment Plan: EAQ201 Study Chair or her designee will present the EAQ201 study to TMIST participating sites via standing TMIST Open Sites calls and through

direct email outreach to site TMIST PIs and lead TMIST research coordinators. This introduction to the study is expected to occur as close as possible to EA activation of the trial. The purpose of the study, site responsibilities, survey team responsibilities, and timeline will be presented on these calls. Along with materials to help support recruitment effort including phone script, study talking points, FAQs to help sites understand the study and to be able to communicate it to potential participants.

All EA1151 participating sites in the United States that are approved to enroll to EA1151 according to CTSU and actively recruiting and enrolling new participants to EA1151 based on at least one new enrollment attributed to the site in the most recent CTSU monthly enrollment report will be cleared to activate EAQ201 by ECOG-ACRIN upon obtaining EAQ201 NCI CIRB approval.

EAQ201 project manager will create a list of eligible sites based on EA1151 recruitment and enrollment status and will notify CTSU of ECOG-ACRIN clearance of this site qualification criteria. Site submission of required IRB documentation to NCI CIRB will be monitored in RSS weekly by the EAQ201 project manager who will report site activation clearances in CTSU weekly to the EAQ201 study chair by [define weekly communication mechanism you prefer here]. All sites that plan to open EAQ201 are strongly encouraged to activate EAQ201 within 30 days of ECOG-ACRIN activation of the trial as there will be no maximum number of subjects that can be enrolled in the trial at any one site and enrollment is expected to be completed within a few months.

EAQ201 project manager will reach out weekly to all eligible EA1151 sites to remind them about the EAQ201 study and obtain IRB approval through NCI CIRB. This outreach will occur by email to TMIST PI and TMIST lead coordinator until the site opens EAQ201, declines to participate, or EAQ201 enrollment reaches 50% of planned enrollment, 500.

**Participant Recruitment Plan:** All participating EAQ201 TMIST sites will be expected to approach at least 20 women per month in person or over the phone as part of their TMIST recruitment effort while EAQ201 is open to participant enrollment with at least 5 women approached that are classified as Women of Color [definition] according to information documented in the site's electronic medical record system.

All women presenting for screening mammography who meet the eligibility criteria for EA1151 but ultimately decline to participate in EA1151 should be immediately invited to participate in EAQ201 by EA1151 site designated recruiters.

All EAQ201 TMIST sites are expected to keep local TMIST recruitment logs for duration of EAQ201 enrollment period. The first two weeks of local TMIST recruitment logs for each site are to be submitted to the EAQ201 project manager to confirm that recruitment effort is happening for TMIST and to monitor number of WOC TMIST declines at the site. This information will be summarized across all sites for reporting to the EAQ201 central trial team to compare to EAQ201 enrollment rates at each site to determine if site is on track to complete within timeline planned and that overall WOC versus non-WOC participation ratio is within 10%-25% range planned.

**Survey administration and data collection:** We will use the ECOG-ACRIN Systems for Easy Entry of Participant Reported Outcomes (EASEE-PRO), our online survey platform supplemented by paper and/or telephone surveys using methods successfully employed in EAQ162CD financial burden assessment in colorectal cancer ([name] co-PI) and E4112 prospective study of MRI and multiparameter gene expression assay in DCIS ([name] co-I). Proxies are not allowed to complete questionnaires on behalf of participants. However, participants may use assistance and other accommodations to

complete questionnaires, including: CRAs, participant navigators/advocates, family members, and/or other individuals or aids that allow the participant to understand and record their answers to the survey questions (for example, visually impaired individuals may have questions read to them and their responses recorded). The surveys are available only in English.

TMIST site RAs will collect contact information at EAQ201 enrollment using Participant Contact Information Forms (name, home address, phone number and e-mail) and fax it to the central ECOG-ACRIN OEAU at Brown University. The COVID factors survey may be completed at the screening visit by paper or online. We assume that 40% will opt to complete the survey after the screening visit based E4112 patient preferences. Those who elect to complete the survey after the screening visit will only be able to do so online to conform to the scope of a supplement. These women will receive an invitation and account activation email from the central ECOG-ACRIN Outcomes and Economic Assessment Unit (OEAU) within 7 days to complete the online survey. Each online participant will use a unique account to complete the survey.

Women who choose to complete their survey online either during or after the screening visit will use our EASEE-PRO web-based participant-facing system. Through EASEE-PRO, study staff communicate with participants about study participation (e.g., email solicitations to logon and complete the survey using unique links and reminders). All study participants can access EASEE-PRO with a valid email address. Upon enrollment into the study, women will be able to activate their account using their email address, either in person or remotely. Activation requires entry of verification information (e.g., DOB) in order to complete activation. TMIST site RAs with the appropriate study roles will be granted access allowing them to assist participants who experience any difficulty. The web site includes a study-specific toll-free phone number to contact OEAU staff for assistance. All data will be stored on a secure server. Participants who do not complete the web surveys within 3 working days of initial e-mail request will receive up to 3 additional e-mail reminders, each 3 days apart. These reminder e-mails provide a link to the current surveys, ask the participant to confirm that they have been able to access the web site and provide both the e-mail address and the toll-free help number for support. All surveys will remain available for participants until either completed or participants are off-study. Since the completion date is recorded for all surveys, the study team will determine appropriate inclusion of these data in specific analyses. If a participant is non-compliant, the OEAU may contact the site CRA and/or the participant in an effort re-establish contact, remove barriers, and obtain the survey responses. These efforts may include email, mail, and phone contact with no more than 3 attempts by any method (i.e., three failed recovery attempts, at least 3 days apart, will be considered participant refusal.)

Women who choose to complete their surveys on paper at the site, should be provided with a paper copy of the survey to complete. The site personnel may then enter the answers into EASEE-PRO. Alternatively, the questionnaire may be faxed to the OEAU. Also, the CRA may have the participant complete the questionnaire on a site-provided tablet or computer.

Outcome and moderator measures are summarized in Table 1 and 2. Participant survey burden in EAQ162CD was 3.25–5.18 questions per minute. The approximately 60 item survey is estimated to take 12-18 minutes.

TABLE 1 : Participant-completed items	
Primary Endpoints	Measure (collected from EAQ201 participants)
COVID-related financial hardship among EAQ201 participants	Composite outcome, defined as answering in the affirmative to any of the following personal changes due to COVID: layoff or furlough, insurance loss, work hours reduction, new job/increased hours to increase income, food or housing insecurity (items used in EAQ162CD) OR answering in the affirmative to any of the following household changes due to COVID: ≥20% income loss, savings use for living expenses, home sale/refinance, increased debt, declared bankruptcy (items used in EAQ162CD)
Secondary Endpoints	Collected from EAQ201 participants
Material condition composite measure	Self-reported material condition of any of the following: >20% income loss, savings use, home sale or refinance, loans, reaching credit limits, becoming subject to a collection agency, or bankruptcy in the last 3 months (binary) (1 item, used in EAQ162CD)
COVID-specific perceived financial distress	Adapted from the summary item from COST measure.  (continuous) “COVID-19 has been a financial hardship to my family.” (1 item)
Exploratory Endpoints	Collected from EAQ201 participants
Employment change	Self-reported work hours reduction, layoff or furlough, sick time or vacation time use or new job/increased hours to increase income (binary) (1 item, used in EAQ162CD)
COVID-specific perceived distress	Adapted from [name] (personal communication) to capture the emotional response to COVID related to fear of infection, financial anxiety, housing and food insecurity (single items). (categorical)(11 items)
Perceived susceptibility to disease	Single items for breast cancer and COVID-19, modified from previous studies of intention to undergo breast cancer screening and used in EA2185 and EAQ162CD. (categorical) (2 items)
Distress coping behavior that increase breast cancer risk	We previously demonstrated that risky behaviors (e.g., cancer screening adherence, not smoking and seatbelt use  ). Alcohol  use has been described a risk factor for breast cancer. Smoking  has been raised as a risk factor. We will assess change in frequency or amount of tobacco or alcohol use during COVID compared to before COVID. We will not assess absolute amount of use. (categorical) (2 items)
HRQL	Participant-Reported Outcomes Measurement Information System (PROMIS)-10  10-item physical and mental health assessment. Sum of item responses (continuous) (10 items)
General anxiety	PROMIS Anxiety 4-item Short Form. Sum of item responses (continuous) (4 items)
Depression	PROMIS Depression 4-item Short Form. Sum of item responses (continuous) (4 items)
Covariates	
Sociodemographics collected from EAQ201 participants	Race/ethnicity, age, education, marital status, annual household income, insurance, ZIP+4* to estimate neighborhood SES the using the Area Deprivation Index 
Sociodemographics collected from women who participate in TMIST	Race/ethnicity, age, insurance, and ZIP

TABLE 1 : Participant-completed items	
Provider-initiated delay	Participant-reported provider-initiated service delay or reduced access for any health service and for screening mammography in the last 3 months due to COVID
TABLE 2: Study team collected items	
Federal-, State- and local-level	Medicaid coverage policies, COVID burden and shelter-in-place policies (initiation, duration and extent of implementation) including any changes during the study period. Local unemployment rates  during shelter-in-place estimated from ZIP+4 using Local Area Unemployment Statistics from the Bureau of Labor.

State-level variables: COVID burden is assessed as:

- 1) Maximum new cases and deaths reported in one day as of registration of the first participant in that state;
- 2) Total case numbers in the 3-month period following the World Health Organization classification as a pandemic on 3/11/20 (raw and population-adjusted values);
- 3) Number of days from 3/11/20 to peak single-day report of new cases;
- 4) Occurrence of a “second peak” defined as a subsequent wave of new cases from the previous maximum number of new cases;
- 5) Cumulative death/infection rates at the time of study activation.

This data will be derived from the states’ departments of health and the Centers for Disease Control and Prevention. We will also examine state statutes and regulations including:

- 1) Timing of initiation of shelter-in-place policies (defined as the number of days from 3/11/20);
- 2) Duration of policies (number of days from initiation to any relaxation of shelter-in-place policies); and
- 3) Medicaid coverage of COVID-related care.
- 4) Shelter-in-place policy extent will be categorized as high (closure of all businesses except essential services e.g., grocery stores and pharmacies) or low (any business closure less complete than the above definition).
- 5) State legislation/regulation searches through Lexis-Nexis will be conducted using methods we previously employed to describe Medicaid coverage of trial participation costs.

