#### **4.1 Registration Demographics**

The following information is to be provided at the time of registration to the trial:

- 4.1.1 Protocol Number
- 4.1.2 Investigator Identification
  - Institution and affiliate name
  - Investigator's name
- 4.1.3 Participant Identification

- Participant's initials (first and last)
- Participant's Hospital ID and/or Social Security number
  - Sex
  - Birth date (mm/dd/yyyy)
  - Race
  - Ethnicity
  - Nine-digit ZIP code
  - Method of payment
  - Country

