### 7.4 Assess the effects of sociodemographic characteristics, and federal-, state- or local-level COVID-19 factors on TMIST participation, in WOC vs non-WOC.

For the exploratory objective ([7.1.3.5](#)), we will compare the effects of sociodemographic characteristics, federal-, state- or local-level factors (e.g. maximum number of COVID-19 cases, state unemployment during shelter-in-place, local unemployment during shelter-in-place) on TMIST participation, stratified by WOC vs non-WOC. We will fit a logistic regression model with TMIST participation status (EAQ201 participant or TMIST participant) as the response variable to investigate other sociodemographic (e.g., marital status, neighborhood SES, insurance type), federal-, state- or local-level factors (see **Table 2**). Regression modeling will be conducted with and without stratification by WOC vs non-WOC.

The analysis set will include the 1000 EAQ201 participants from this study and a corresponding number of TMIST participants, who will be randomly selected from the enrolled participants in the main TMIST study. The selection will be stratified by site and enrollment time. Assuming that the proportion of overall EAQ201 participants is from 0.20 to 0.50, **Table 5** below shows the power analysis of testing for the odds ratio in the logistic regression. The variables of interest can be continuous or categorical (binary). For instance, 2000 women (1000 EAQ201 participants versus 1000 randomly selected TMIST participants) achieves 90% power at a 0.050 significance level to detect a change in the proportion of EAQ201 participants from 0.50 at the mean of the testing variable to 0.538 when the value of the variable is increased to one standard deviation above the mean. This change corresponds to an odds ratio of 1.165. An adjustment was made since a multiple regression of the independent variable of interest on other independent variables in the logistic regression obtained an R-Squared of 0.10.

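### Section 5 limits the EAQ201 side of the TMIST comparison to survey completers, although race/ethnicity, age and ZIP are held for every registrant and 7.3 and 7.4 refer to EAQ201 participants

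*Combined protocol and SAP*

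**What the plan says.** Section 5 plans to "compare the sociodemographic characteristics of women who complete the EAQ201 participant survey with women who agree to participate in TMIST", with the TMIST women taken from the same period. The variables are limited to those that both studies hold; the comparison is to be made "using only data collected as part of the TMIST study that have also been collected as part of the current study". On the TMIST side Section 5 adds: "No additional data will be collected from women who participate in the TMIST study". The covariate block of Table 1 lists the TMIST items as "Race/ethnicity, age, insurance, and ZIP".

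Section 4.1 opens its list with "The following information is to be provided at the time of registration to the trial". Under 4.1.3 that list includes birth date, race, ethnicity, "Nine-digit ZIP code" and method of payment. The footnote to Table 3 (Section 6) confirms that some sociodemographic items come from registration and not from the questionnaire.

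The statistical sections describe the EAQ201 group differently. Section 7.3 compares the WOC share in EAQ201 participants with that in TMIST participants. Section 7.4 says: "The analysis set will include the 1000 EAQ201 participants from this study", with a random TMIST sample stratified by site and enrollment time. Neither mentions survey completion.

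Non-response is foreseen. Section 5 assumes that 40% will defer the survey until after the visit and treats three failed recovery attempts as refusal. Section 7.5 allows that missingness may be informative.

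**The concern.** Under the Section 5 sentence, an EAQ201 woman is counted only if she registers and then finishes a survey. A TMIST woman is counted once she enrolls. Any link between finishing the survey and race, age or area therefore enters the contrast from one side and has nothing to do with the decision about TMIST.

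For variables already recorded at registration, this selection is avoidable. What is at stake directly is the Section 5 descriptive comparison. Indirectly, it is objectives 2.2.3 (WOC share) and 2.3.5 (model of TMIST participation), should an analyst take Section 5 as the definition of the analysis group. The plan's own reasoning makes unequal completion plausible: 7.5 suggests that women lost may carry more financial burden, and 7.1.1 hypothesizes more hardship in WOC.

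**Working it through.** **Step 1. Which compared variables need the survey?**

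| TMIST item (Table 1) | EAQ201 source at registration (4.1.3) | Known for every registrant? |
|---|---|---|
| Race/ethnicity | Race; ethnicity | Yes |
| Age | Birth date | Yes |
| ZIP | Nine-digit ZIP | Yes |
| Insurance | Method of payment only; the survey has a separate insurance block of 4 to 8 questions (Table 3) | Only if the two items are equivalent, which the documents do not say |

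**Step 2. Reproduce the plan's figure.** Section 5 has no test or power of its own. The only stated figure for an EAQ201-versus-TMIST contrast of a sociodemographic variable is in 7.3: reference share 25%, two-sided exact test at 0.05, 80% power for 3.9 points. Section 7.3 states no n, so I take the 1,000 of 7.2. The equal-tailed exact binomial test rejects at 222 or fewer, or 278 or more (actual size 0.0445). Power is 78.8% at 28.9% and 81.4% at 21.1%. The stated 80% reproduces.

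**Step 3. What a completer filter would do if applied to that test.** With true WOC share w and completion rates cW (WOC) and cN (non-WOC):

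share among completers = w·cW / (w·cW + (1 − w)·cN); completers = 1,000 × (w·cW + (1 − w)·cN).

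All completion rates below are assumptions. With w = 0.25, equal to the TMIST reference:

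| cW / cN | WOC completers / all completers | Share | Probability that the 7.3 test rejects |
|---|---|---|---|
| 80% / 80% | 200 / 800 | 25.0% | 5% |
| 93% / 95% | 232.5 / 945 | 24.6% | 5% |
| 90% / 95% | 225 / 937.5 | 24.0% | 11% |
| 80% / 90% | 200 / 875 | 22.9% | 30% |
| 75% / 85% | 187.5 / 825 | 22.7% | 31% |
| 70% / 85% | 175 / 812.5 | 21.5% | 62% |

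The direction follows the sign of the gap. Reversing 75/85 to 85/75 gives 212.5 / 775 = 27.4%.

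**Step 4. Effect on a true difference.** The hypothesis in 7.1.2.3 is a higher WOC share among decliners. With w = 0.289, power is 79% using all 1,000 registrants. Using completers it is 70% at 80/80 (loss of n only), 49% at 90/95, 17% at 80/90 and 14% at 75/85.

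**Step 5. The plan's own share for decliners.** Section 7.2 reports that 16% of women who declined TMIST were WOC. With w = 0.16, the completer share is 120 / 834 = 14.4% at 75/85 and 112 / 826 = 13.6% at 70/85. Against 25% the test rejects essentially always, with or without the filter.

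**The case against.** The strongest reply is that the sections governing the objectives do not contain the restriction. Objective 2.2.3, 7.1.2.3, 7.3 and 7.4 all refer to EAQ201 participants. Sections 4.3.5 and 5 also use the word participant for women who have not yet completed the web survey. The Section 5 sentence cites neither objective. This stands. A reader might infer that the secondary WOC-share test is planned on completers and so carries a false-positive rate of 31% to 62%. The documents do not support that: the effect on 2.2.3 and 2.3.5 is a risk from two definitions in one document.

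A reader might also infer that completers are set against all TMIST enrollees, or that every compared variable is available at registration. Neither is right. Section 5 limits TMIST women to the same period and 7.4 samples them. Insurance is held at registration only as method of payment. Section 7.4 also names marital status, which is not in the registration list. It is not among the TMIST items in Table 1 either, so it falls outside the Section 5 comparison.

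The larger completion gaps can fairly be called severe. If the 60% who do not defer all complete (an assumption), then 75% against 85% overall needs (0.75 − 0.60)/0.40 = 37.5% against (0.85 − 0.60)/0.40 = 62.5% among deferrers. Reminders and recovery contacts are planned. Hence the mild and null cases in the table matter as much as the severe ones.

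Finally, consent to EAQ201 and the English-language requirement (3.1.2) also select decliners, and using all registrants does not remove that. This is true, but it is no reason to add a further, avoidable filter.

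**Conclusion.** The point holds for the Section 5 sentence. It restricts one side to survey completers, conflicts with the wording of 7.3 and 7.4, and is unnecessary for race/ethnicity, age and ZIP. The consequence for 2.2.3 and 2.3.5 is conditional on analysts adopting the Section 5 definition.

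In that case, with a true share of 25%, the shift ranges from none (equal completion) through 0.4 points (93/95) and 1.0 point (90/95) to 3.5 points (70/85), against a planned detectable difference of 3.9 points. These figures rest on assumed completion rates; the documents give none, overall or by race, so the size and direction of any real bias are unknown. If completion is unrelated to race, the WOC share is unbiased and only sample size is lost. If the true share is near the 16% quoted in 7.2, the test result would be the same, though the estimate could still move.

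The correction is worth making because it removes a one-sided selection at almost no cost.

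**What to change.** - In Section 5, define the EAQ201 side of the comparison as all eligible women registered to EAQ201. Take race/ethnicity, age and ZIP from the registration record.
- In 7.3 and 7.4, state that EAQ201 participants means the same group, so that the three sections agree.
- For insurance, use the registration method of payment only if it matches the TMIST insurance item. Otherwise use the survey item and handle its missing values under 7.5.
- Keep completers only for endpoints that come from the survey.
- Report completers against non-completers on the registration variables, so that survey selection is visible.
- Note as a limitation that selection by consent to EAQ201 and by the English-language requirement remains.

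The cost is a few sentences in Section 5 and Section 7 and one descriptive table. No new data are collected.
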